8.6 Derived and Computed Variables

All derived and computed variables will be outlined in the analysis dataset specifications for this study. These datasets are independently programmed by two statisticians. The SAS COMPARE procedure will be used to verify that the dual programmed analysis datasets are identical for each variable and each observation.

9. STUDY SUBJECTS

9.1 Disposition of Subjects and Withdrawals

All eligible subjects who provide informed permission will be accounted for in this study. The frequency and percent of subjects in each population, study withdrawals, subgroups, and major protocol violations will also be presented. While the final definition of “major protocol violation” will be determined during the course of the trial, in all instances randomizations of subjects who were later found not to meet eligibility criteria, and instances where subjects received the opposite of the assigned treatment or did not receive PRK after randomization will be reported in the subject disposition reports.

10. EFFICACY ANALYSES

10.1 Primary Efficacy Variable Analysis

The analysis of the primary study outcome will include the following test of hypothesis:

H_0 : time to re-epithelialization is not different among eyes receiving treatment with pAF after PRK, compared to eyes receiving placebo drops after pRK.

The alternative hypothesis is:

H_1 : time to re-epithelialization is significantly different among eyes receiving treatment with pAF after PRK, compared to eyes receiving placebo drops after pRK.

For testing the primary hypothesis, a mixed effects linear model with time to re-epithelialization (number of calendar days from PRK to time to complete re-epithelialization) for each eye as outcome, and assigned treatment arm as a predictor will be fit using SAS PROC MIXED. This model will additionally include a random effect for each patient (formally included in the model as each patient’s study ID, defined as a CLASS variable) to model correlation between eyes in the same participant. A two-sided probability value with an alpha level of 0.05 will be used to test the null hypothesis that time to re-epithelialization is not different between the two treatment arms. If the probability value is less than 0.05, regardless of the direction of treatment effect, the null hypothesis above will be considered to be rejected.

The primary analysis will be performed on an intention to treat basis.

All eyes with available outcome data will be included in the model. Any eyes that are not completely re-epithelialized by Day 8 will be assigned a value of 9 days to re-epithelialization in the primary analysis. Any eyes for which time to re-epithelialization is not fully known due to missed visits will be assigned the midpoint of the possible time in the primary analysis (for example, a patient not re-epithelialized in either eye on Day 2, who misses visits on Days 3 and 4 but has complete re-epithelialization in both eyes on Day 5, would be treated as having complete re-epithelialization in both eyes on Day 4 in the primary analysis). Eyes of patients who drop out of the study before Day 8, that do not achieve complete re-epithelialization before dropout, will be treated as missing in the primary analysis, but included in robustness analyses described below.

Results of the analysis above will be accompanied by appropriate presentation (e.g., histograms) of the distribution of number of calendar days to complete re-epithelialization among eyes in each treatment arm.

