5.1 Schedule of Events

| | Baseline | Day of Surgery (Friday) | | Days after Surgery | | | | | | | | | | |
|--|----------|----------------------------|---|--------------------|--------|--------|--------|--------|---------------------------------------|----------------------------|----------------------------|-----------------------------|------------------------------|---|
| | | Day 1 (AM) | Day 1 (2 nd visit post- surgery) | Day 3 | Day 4* | Day 5* | Day 6* | Day 7* | Day 8 Friday AM (in-person visit)* | Month 1 (Day 30±10)* | Month 3 (Day 90±14)* | Month 6 (Day 180±30)* | Month 12 (Day 365±30)* | |
| Informed Consent | X | | | | | | | | | | | | | |
| Eligibility | X | | | | | | | | | | | | | |
| Medical History | X | | | | | | | | | | | | | |
| Concomitant medications ² | X | X | X | X | X | X | X | X | X | X | X | X | X | |
| Randomization ³ | | | X | | | | | | | | | | | |
| PRK Surgery | | | X | | | | | | | | | | | |
| Dispense Masked Study Drug ⁴ | | | X | | | | | | | | | | | |
| Study Drug Compliance ⁵ | | | | X | X | X | X | X | | | | | | |
| Pain Assessment ⁶ | | | | X | X | X | X | X | | | | | | |
| Size of Epithelial Defect ⁷ | | | X | | X | X | X | X | X | | | | | |
| Uncorrected VA ⁸ | X | | | | | | | | | X | X | X | X | X |
| Manifest Refraction | X | | | | | | | | | | X | X | X | X |
| Target Post-OP Refraction | X | | | | | | | | | | | | | |
| BCVA ⁸ | X | | | | | | | | | | X | X | X | X |
| Ocular Surface Staining | X | | | | | | | | | | X | X | X | X |
| Corneal Topography | X | | | | | | | | | | X | X | X | X |
| Ocular Adverse Events | | | | X | X | X | X | X | X | | X | X | X | X |

1. The pre-op screening/baseline visit may be performed in 2 separate visits.

2. Record systemic medications at baseline and any subsequent changes; Record start and stop dates of ocular medications prescribed as standard care post-PRK surgery, note any deviations from prescribed regimens.

3. Randomization to study drug assignment will occur when patient presents day of surgery.

4. First dose of study drug applied to each eye at completion of surgery. Three additional doses administered by patient on day of surgery, then 4x per day through Day 7.

5. Patient will document each use of study drug and oral pain medication in diary.

6. Patient will assess highest level of daily pain/discomfort at the end of each day.

7. Grade defect dimensions until healed.

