3.2 Study Endpoints

3.2.1 *Primary Efficacy Endpoint*

The primary efficacy endpoint of the pAF after PRK trial is the number of calendar days from PRK to complete re-epithelialization, evaluated in all PRK-treated eyes among enrolled patients.

Time to re-epithelialization will be measured from the end of surgery until the date of the exam where complete re-epithelialization is observed. While specific evaluation times will be collected, since the time of surgery and the time of the follow-up exam are dependent upon scheduling, time to re-epithelialization will be analyzed as an integer, being simply the number of calendar days from the day of surgery to the date of the first examination demonstrating complete re-epithelialization.

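### The SAP's midpoint rule has no Day 8 limit, so an eye that misses the Day 8 examination can be assigned about 18 days while an eye known to be unhealed on Day 8 is assigned 9

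*SAP*

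**What the plan says.** SAP 10.1 handles incomplete healing times in the primary analysis with three rules.

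- Late healing: "Any eyes that are not completely re-epithelialized by Day 8 will be assigned a value of 9 days to re-epithelialization in the primary analysis".
- Missed visits: "Any eyes for which time to re-epithelialization is not fully known due to missed visits will be assigned the midpoint of the possible time". The one example is a patient unhealed on Day 2 who "misses visits on Days 3 and 4 but has complete re-epithelialization in both eyes on Day 5" and "would be treated as having complete re-epithelialization in both eyes on Day 4 in the primary analysis".
- Dropout: "Eyes of patients who drop out of the study before Day 8, that do not achieve complete re-epithelialization before dropout, will be treated as missing".

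SAP 3.2 defines the endpoint as "the number of calendar days from the day of surgery to the date of the first examination demonstrating complete re-epithelialization". It sets no last day on which such an examination counts.

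The Protocol (section 5) counts the day of surgery as Day 1 and schedules defect measurement on Days 1 and 3 to 8. The next visit after Day 8 is given in Protocol 5.1 as "Month 1 (Day 30±10", that is, Day 20 to Day 40. A footnote to that table asks for the defect to be graded until it has healed.

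**The concern.** Consider an eye unhealed on Day 7, not examined on Day 8 and seen healed at Month 1. The patient has not dropped out, so the dropout rule does not apply. The eye was not observed unhealed on Day 8, so the 9-day rule does not clearly apply. What remains is the midpoint rule, and the possible time then runs from Day 8 to the date of the Month 1 visit.

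The result is in the wrong order. An eye that may have healed on Day 8 receives about twice the value of an eye known to be unhealed that day. How far it exceeds 9 depends on when in a 20-day window the patient returns, which says little about healing. The value then enters a linear mixed model planned around a standard deviation of 0.5 to 0.7 day, where a single extreme patient carries weight in both the estimate and the residual variance.

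**Working it through.** **1. The plan's own figures.** Inputs from SAP 6: 28 patients (56 eyes) per arm, SD 0.6, ICC 0.6, two-sided alpha 0.05. Detectable difference = (z for alpha + z for power) × SD × √(2(1 + ICC)/56).

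- 80% power: (1.960 + 0.842) × 0.6 × √(3.2/56) = 0.40 day (SAP table: 0.41).
- 90% power: (1.960 + 1.282) × 0.6 × √(3.2/56) = 0.46 day (SAP table: 0.47).

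A t version with 54 degrees of freedom gives 0.41 and 0.47, so the table reproduces. At the 0.5-day target, power under these assumptions is about 93%.

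**2. The midpoint convention.** Taking the possible days as those after the last unhealed examination up to the first healed one, the SAP example gives (3 + 5)/2 = Day 4, as stated.

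**3. The same rule for an eye unhealed on Day 7 and healed at Month 1.** Calendar days are study day minus 1, because surgery is Day 1.

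| Month 1 examination | Midpoint (study day) | Calendar days |
|---|---|---|
| Day 20 | (8 + 20)/2 = 14 | 13 |
| Day 30 | (8 + 30)/2 = 19 | 18 |
| Day 40 | (8 + 40)/2 = 24 | 23 |

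For a Day 30 visit, other numbering conventions give 17.5 to 19. The case is not confined to eyes unhealed on Day 7: an eye last seen unhealed on Day 3 and next examined on Day 30 gets (4 + 30)/2 = Day 17, or 16 calendar days.

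**4. Shift in the arm mean attributable to the rule.** The comparator is the 9 days given to an eye seen unhealed on Day 8.

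| Assigned value | Both eyes of one patient, (value − 9)/28 | One eye, (value − 9)/56 |
|---|---|---|
| 13 | 0.14 day | 0.07 day |
| 18 | 0.32 day | 0.16 day |
| 23 | 0.50 day | 0.25 day |

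**5. Effect on power (illustrative).** Assumptions: placebo mean 3.6, pAF mean 3.1, SD 0.6, ICC 0.6, 28 patients per arm, t-test on patient means, 20,000 simulated trials, one patient's value fixed. The expected estimates follow by arithmetic, for example 0.5 + (18 − 3.6)/28 = 1.01.

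| Affected patient (both eyes) | Value | Expected estimate of benefit | Power |
|---|---|---|---|
| None | – | 0.50 | about 93% |
| One, placebo | 9 | 0.69 | about 92% |
| One, placebo | 18 | 1.01 | about 36% |
| One, pAF | 9 | 0.29 | about 5% |
| One, pAF | 18 | −0.03 | about 0% |

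With only one eye of a placebo patient affected, power goes from about 95% at 9 to about 88% at 18. In the placebo arm the estimate doubles while power falls, because the one value inflates the variance more than it moves the mean.

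**The case against.** The strongest reply is that the 9-day rule comes first in the paragraph and refers to eyes not healed by Day 8, not to eyes seen unhealed on Day 8. An eye with no healed examination by Day 8 can be read into it, and the only midpoint example lies in the first week. That reading may be what was intended. It is not written, however, and the two independent programmers foreseen in SAP 8.6 could code the eye differently.

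Second, the case is rare. With a mean of 3.6 and SD 0.6, a normal model puts the chance of a healing time beyond 6 calendar days at about 3 in 100,000 (about 3 in 10,000 at SD 0.7). The Protocol requires a Day 8 visit, asks for grading until healed, does not list defect size at Month 1, and allows extra safety visits. This stands, with limits. Real tails may be heavier, and SAP 10.1.1 itself allows for eyes unhealed at Day 8. The Day 8 column, though labelled in-person, carries the footnote permitting telehealth or phone contact, which cannot supply a slit-lamp measurement.

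Third, there are safeguards: outlier review, a blinded data review, histograms and a clustered log-rank analysis, in which a late value has little leverage. But SAP 8.2 keeps valid outliers, and the log-rank analysis is supportive and gives no rule for this eye.

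A reader might also infer that one missed visit moves the arm mean by (18 − 3.5)/28 = 0.52 day, more than the whole target effect. The documents do not support charging all of that to this rule: (9 − 3.5)/28 = 0.20 day would arise under the 9-day rule anyway.

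**Conclusion.** The gap is real. As written, SAP 10.1 can give an eye of unknown Day 8 status about 18 calendar days (13 to 23), against 9 for an eye known to be unhealed that day. For one patient with both eyes affected, the excess is about 0.32 day in a 28-patient arm mean (0.14 to 0.50), and half that for one eye, against a 0.5-day target. The sizes rest on the literal reading, the Month 1 window and 28 completers per arm; the power figures rest also on the simulation assumptions.

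Two stronger conclusions should not be drawn. It is not established that the rule will decide the primary result: the case should be rare and a capped reading is open. Nor does the rule cause most of the power loss when the affected patient is in the pAF arm: with both eyes at 9 days power is already about 5%, so a cap cures the ordering but not that sensitivity. It would also be wrong to say that the differently treated eyes hold the same information, since one of them was actually observed unhealed on Day 8.

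**What to change.** Amend SAP 10.1 before unblinding:

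1. Apply the midpoint rule only where the gap is bracketed by two defect examinations within Days 1 to 8.
2. State that any eye of a patient still in the study that is not documented healed by Day 8 is assigned the same 9 days as an eye seen unhealed on Day 8, whatever the date of the later examination.
3. Leave the dropout rule as it is, but say that it takes effect only when the patient has left the study, so that every eye falls under exactly one rule.
4. Optionally add an interval-censored analysis with patient clustering to SAP 10.1.1 as a robustness check. It would use what is known about these eyes without a fixed value. That helps most for an eye last seen unhealed early in the week, for which 9 days may be too long.

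The first three changes cost only SAP wording and the matching dataset specification. The fourth adds one supportive analysis. None changes visits, data collection or sample size.

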10.1.1 Robustness Analyses

In this trial, it is possible that some patients may not be fully compliant with the drug administration regimen, some eyes may not achieve complete re-epithelialization by the time of the Day 8 evaluation, and/or that some patients may drop out prior to Day 8 without having achieved complete re-epithelialization in one or both eyes. If any of these circumstances occur, then the following robustness analyses will be carried out:

1. The two treatment arms will be compared by survival analysis approaches. Specifically, the number of calendar days to re-epithelialization will be treated as a time-to-event variable, and any eyes not exhibiting complete re-epithelialization at their final evaluation (including such eyes evaluated on Day 8) will be treated as censored at time of last evaluation. The time to re-epithelialization curves will be compared between the treatment arms using a two-sided log-rank test appropriate for the within-patient clustered nature of the trial data (REF Stedman R et al. A SAS Macro for a clustered logrank test. Computer Methods and Programs in Biomedicine 2011; 104:266-70).
2. The primary analysis, as well as the survival analysis described immediately above, will be carried out as above among evaluable subjects who met all eligibility criteria for the trial and received their assigned treatment (per-protocol efficacy population), if this population differs from the mITT population.

As noted above in this document, in the event that any patients received the incorrect treatment assignment in the circumstances of an isolated “good faith” error, it is proposed that the treatment received be used in the primary reported analysis, although such errors are to be fully disclosed in the publication of trial results.

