4.3 Method of Treatment Assignment and Randomization

Randomization to intervention (pAF or placebo drops) will be performed in a 1:1 ratio, without additional stratification. Randomized blocks of varying lengths will be used to generate the randomization scheme. Smaller block lengths will be used preferentially at the beginning of the generated randomization sequence. Specific block length probabilities are not included in this SAP but will be kept on file at the Coordinating Center, in order to limit predictability of subsequent treatment assignments in case of unblinding. Randomization specifics will be as follows:

1. Two sequences of blocks will be generated using blocks of length 2 and/or length 4, so that the total number of randomizations across the two sequences will be sufficient to achieve the number of randomizations expected in the trial (at least 80). The first sequence will preferentially use smaller block lengths.
2. Within each sequence, the blocks will be permuted as necessary to achieve a fully random permutation of blocks.
3. Each block will then be assigned a random permutation of treatments (for block length 2, a sequence of one of each treatment assignment will be permuted; for block length 4, a sequence containing two of each treatment assignment will be randomly permuted).
4. The final randomization sequence for the trial will be the series of assignments in the first sequence, followed by the series of assignments in the second sequence.

Randomization seeds will be selected and recorded, along with all code used to generate the randomizations, to enable reproducibility of the treatment sequence if necessary.

Randomization sequences will be prepared by the pAF after PRK study biostatistician.

4.3.1 *Handling of Incorrect Randomizations in Study Analyses and Reports*

Any patients who are assigned the incorrect treatment will be given the assigned treatment and treated as such in all analyses (recognizing that extremely rare “good faith” errors of this type may occur and that the cause of any such errors must be immediately rectified). Any such violations are to be reported to the DSMB as part of all reports.

4.3.2 *Delivery of Randomization*

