The sequence of randomizations will be delivered to designated unblinded personnel at the University of Utah’s Cell Therapy and Regenerative Medicine Program (CTRM), who will transcribe the randomization sequence in order to treatment boxes with a sequential masked ID, each of which contains the assigned treatment (study drug or placebo).

Each patient who is consented, and who successfully receives PRK and is fully eligible for the trial in all respects immediately after surgery, will then receive the next available treatment box, in numerical order. Therefore, in this trial, only patients who actually receive a treatment box after surgery will be considered to have been randomized and eligible for intention to treat analysis.

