10.2 Secondary Efficacy Variable Analysis

The analysis of the secondary study outcome will include the following test of hypothesis uncorrected visual acuity, as assessed in each PRK-treated eye on Study Day 30:

H_0 : at 30 days after surgery, uncorrected visual acuity is not different among eyes receiving treatment with pAF after PRK, compared to eyes receiving placebo drops after pRK.

The alternative hypothesis is:

H_1 : at 30 days after surgery, uncorrected visual acuity is different among eyes receiving treatment with pAF after PRK, compared to eyes receiving placebo drops after pRK.

For testing this hypothesis, a mixed effects linear model with the logarithm of uncorrected visual acuity assessed on Day 30 for each eye as outcome, and assigned treatment arm as a predictor will be fit using SAS PROC MIXED. This model will additionally include a random effect for each patient (formally included in the model as each patient’s study ID, defined as a CLASS variable) to model correlation between eyes in the same participant. A two-sided probability value with an alpha level of 0.05 will be used to test the null hypothesis that uncorrected visual acuity at 30 days is not different between the two treatment arms. If the probability value is less than 0.05, regardless of the direction of treatment effect, the null hypothesis above will be considered to be rejected.

Any eyes with uncorrected visual acuity less than 20/400 (e.g., participant is able to detect hand motion only) will be treated as having 20/400 acuity in these analyses, with such (unexpected) instances being explicitly noted in the description of analysis results.

The secondary efficacy analysis will be performed on an intention to treat basis.

Robustness analyses will also be carried out and reported as appropriate (for example, patients with missing data on Day 30 who have not achieved 20/20

uncorrected visual acuity at their last study visit would have their last visual acuity value used in a supportive analysis).

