Primary reporting of Adverse Events will include the Safety Population, and reported overall as well as by the actual treatment that each subject received. Rates of adverse events will be compared between the two treatment groups using chi-squared type approaches. In most instances, exact approaches will be implemented that maximize the statistical power to detect a treatment difference. Specifically, when exact approaches are appropriate, the mid-*p*-value correction¹⁴ will be implemented, whereby the probability value of obtaining a result at least as extreme as observed is reduced by one half of the probability of obtaining the specific result observed. This is directly calculable in SAS, for example, as the Fisher's exact test output gives these two probabilities directly.

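### The primary efficacy analysis is labelled intention-to-treat by assigned arm, but SAP 10.1.1 analyses patients given the wrong product by treatment received

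*SAP*

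**What the plan says.** SAP 10.1 specifies a mixed model for healing time in each eye, "and assigned treatment arm as a predictor will be fit using SAS PROC MIXED", and adds: "The primary analysis will be performed on an intention to treat basis". Protocol 12.1 says the same. SAP 7 defines the intention-to-treat population as all consented, randomised subjects, whether or not they started treatment or followed the protocol.

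The last paragraph of SAP 10.1.1 deals with patients who get the wrong product through an isolated error made in good faith. For them, "it is proposed that the treatment received be used in the primary reported analysis", with disclosure in the publication. It refers back to SAP 4.3.1, which reads: "Any patients who are assigned the incorrect treatment will be given the assigned treatment and treated as such in all analyses".

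The per-protocol robustness analysis is restricted to eligible patients who "received their assigned treatment (per-protocol efficacy population), if this population differs from the mITT population". For the secondary endpoint, SAP 10.2 states: "The secondary efficacy analysis will be performed on an intention to treat basis". Adverse events are "reported overall as well as by the actual treatment that each subject received" (SAP 11.1).

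On when randomisation happens, protocol 5, 5.1 (note 3) and 5.3 place it before surgery or on presentation on the day of surgery. SAP 4.3.2 says that "only patients who actually receive a treatment box after surgery will be considered to have been randomized and eligible for intention to treat analysis".

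**The concern.** A patient analysed by treatment received is not analysed by assigned arm, so for a wrong-product patient SAP 10.1 and 10.1.1 cannot both be followed. Which rule applies turns on whether the error was isolated and made in good faith, and the SAP defines neither term. If the exception is used, the result reported as intention-to-treat would not be one, and the randomised comparison need not appear beside it.

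There is also a lesser, mainly definitional point. The two documents disagree on the moment of randomisation. That moment sets who belongs to the intention-to-treat population, what the disposition table counts, and when the adverse-event window opens (protocol 5.4 starts it at randomisation).

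**Working it through.** **1. The text.** SAP 4.3.1 does not settle the matter. If it means that such patients are analysed by the product they received, the exception covers all analyses, including the secondary endpoint that 10.2 declares intention-to-treat. If it means that they are analysed as assigned, it contradicts 10.1.1, which cites it. Either reading needs an edit.

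**2. Is there a fallback?**
- The per-protocol analysis excludes these patients by definition.
- The clustered log-rank test names no basis for its arms. It is triggered by non-compliance, non-healing by Day 8 or dropout, and wrong product is not listed.
- SAP 9.1 only counts these patients in the disposition report.

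Nothing explicitly restores the randomised arm.

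**3. The plan's own figures.** Inputs from SAP 6: 28 patients (56 eyes) per arm, SD 0.5 to 0.7 days, ICC 0.5 to 0.75, two-sided alpha 0.05, difference 0.5 days. With two eyes per patient, SE = SD × √((1 + ICC)/28). A t calculation with 110 df reproduces all 18 detectable differences in the table to two decimals (for example 0.327 and 0.379 against the stated 0.33 and 0.38). The steps below use 54 df, because patients are the randomised units.

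| SD / ICC | SE (days) | Power at 0.5 days |
|---|---|---|
| 0.5 / 0.5 | 0.116 | 98.9% |
| 0.6 / 0.6 | 0.143 | 92.8% |
| 0.7 / 0.75 | 0.175 | 80.1% |

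**4. Shift from moving one patient.** Take a common mean and one placebo-assigned patient at d days from it. Placebo minus pAF is d/28 by assigned arm and −d/29 by treatment received, so the shift is d/28 + d/29.
- d = 0.6: 0.0214 + 0.0207 = 0.042 days.
- Both eyes take the imputed 9 days. With an assumed mean of 3.35 (midpoint of 3.1 and 3.6), d = 5.65 and the shift is 0.202 + 0.195 = 0.397 days. This is a limiting case: 5.65 days is 8 to 11 SDs at SD 0.7 to 0.5.

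**5. How often the verdict changes.** The number of errors is not in the documents, so one and two are assumed, all of them placebo-assigned patients given pAF. The simulation used 200,000 trials per setting, a true difference of 0.5 days and a t test on patient means, which equals the mixed model when both eyes are observed. Share of trials in which the two rules disagree on p < 0.05:

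| SD / ICC | One error | Two errors |
|---|---|---|
| 0.5 / 0.5 | 1.0% | 1.9% |
| 0.6 / 0.6 | 3.8% | 6.4% |
| 0.7 / 0.75 | 7.1% | 11.0% |

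With one error, the mean estimate is 0.5 × 27/28 = 0.482 days by assigned arm and 0.500 by treatment received. At SD 0.7 and ICC 0.75, power by assigned arm falls from 80.1% to about 77%. Of the 7.1% disagreement there, about 5.1 points are significant only by treatment received and 2.0 only by assigned arm. With no true difference, both rules reject in about 5% of trials.

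**6. Randomisation timing.** Under SAP 4.3.2 nobody is randomised without having had PRK. SAP 9.1 nevertheless plans to report randomised patients who did not receive it, and the modified intention-to-treat definition in SAP 7 makes PRK a separate condition. Under 4.3.2 the first cannot occur and the second is redundant.

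**The case against.** The rule is written in advance, worded as a proposal, and limited to isolated errors. Masking, DSMB reporting and disclosure in the publication surround it. The trial's primary objective is safety, and safety reporting is already by actual treatment. The disagreement rates are conditional on errors having occurred, all in one direction, with a true effect. Most of the disagreement is dilution in the assigned-arm analysis rather than error in the other. The hypotheses in SAP 10.1 are themselves worded in terms of eyes receiving each product. If a masked box is simply handed out of order, one could argue that the box received is the randomisation.

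Most of this stands as a limit on size. It does not remove the contradiction: masking and disclosure reveal an error but do not supply the randomised comparison, and dilution is a known property of the analysis the SAP says it is using. The out-of-order case supports defining the assigned arm explicitly. SAP 4.3.2 already gives the basis, since boxes are issued in numerical order. It is fair to say that the exception reaches the secondary endpoint only on one reading of 4.3.1, and that the timing point hardly touches the primary estimate, because an eye without PRK has no healing time.

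**Conclusion.** The concern holds and should be fixed. The primary efficacy analysis is not uniquely defined for wrong-product patients, and under SAP 10.1.1 the reported result would not match its intention-to-treat label. The practical size is nil without an error and modest with one or two: a shift of about 0.04 days for a patient 0.6 days from the mean, and a changed verdict in 1.0% to 11.0% of trials over the settings examined. Those percentages assume 28 patients per arm, a true 0.5-day difference and one or two one-way errors. The unconditional figure is smaller but cannot be given, because the documents state no error rate. Type I error is not inflated if errors are unrelated to prognosis, and safety reporting is unaffected. The timing conflict is secondary and bears on definitions and counts.

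**What to change.** Replace the last sentence of SAP 10.1.1 and reword 4.3.1 to match. Primary and secondary efficacy analyses should use the arm assigned by the randomisation sequence, meaning the arm of the numbered box due to that patient. Treatment received should be used only for safety and for a labelled sensitivity analysis. The good-faith judgement then no longer decides which dataset is primary.

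For the secondary point, state one moment of randomisation in both documents, consistent with how boxes are actually allocated:
- If it is box receipt after surgery, amend protocol 5, 5.1 note 3 and 5.3, and remove the no-PRK wording from SAP 9.1 and the PRK condition from the modified intention-to-treat definition.
- If it is before surgery, rewrite SAP 4.3.2 so that each patient is tied to a box number, and so to an arm, at that time.

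Then align the population, disposition and adverse-event start definitions.

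The cost is one sentence in each of two SAP sections, plus a few wording changes across both documents for the timing point. No new data are needed and the sample size does not change.
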